1. PROTOCOL SUMMARY

1.1. Synopsis

Protocol Title:

A Phase 4, Multicenter, Open-label, Single-arm Study of Safety, Tolerability, Effectiveness and Treatment Optimization in Participants Switching From Xyrem to XYWAV for the Treatment of Narcolepsy

Brief Title:

An Interventional Safety Switch Study (IS3) of XYWAV in Narcolepsy

Rationale:

XYWAV has been approved in the United States (US) for the treatment of cataplexy or excessive daytime sleepiness (EDS) in patients 7 years of age and older with narcolepsy ([XYWAV US Prescribing Information \[USPI\] 2020](#)).

The rationale for the interventional, open-label, single-arm design of Study JZP258-401 is to evaluate the clinical experience in participants with narcolepsy transitioning treatment from Xyrem to XYWAV, through achieving the following key objectives:

- Provide descriptive evidence of safety, tolerability, effectiveness and treatment optimization during switching of Xyrem-stable participants to XYWAV
- Demonstrate that a range of effectively treated Xyrem participants can be effectively switched to XYWAV
- Explore dosing and administration instructions to support an initial conversion to XYWAV on a gram-per-gram basis as Xyrem. Once the investigator determines that a stable dose and regimen is achieved, XYWAV may be taken with or without food. If needed, XYWAV will be titrated to an optimized dose and regimen based on efficacy and tolerability, under the advisement and instruction from the investigator.
- Expand the body of knowledge of clinical experience of participants switching from Xyrem to XYWAV with regard to safety, tolerability, effectiveness and treatment optimization for XYWAV

The study design will enable weekly assessments of participants to gain an understanding of participant experience during switching from Xyrem to XYWAV. A repeated (weekly) visit design has been utilized to provide frequent data points as participants proceed through treatment conversion and optimization process with XYWAV.

An extended 2-week ‘Baseline’ period during which participants will remain on their currently prescribed, baseline Xyrem dose and regimen has been included to collect additional baseline data. The open-label design of this study is deemed appropriate for this purpose, as the efficacy of XYWAV was previously established in a controlled, phase 3 clinical study (15-006) supporting the approval of XYWAV for the narcolepsy indication.

To build on the existing knowledge base of XYWAV, investigators will instruct participants to initially transition from Xyrem to XYWAV at the same dose and regimen as Xyrem. Once the investigator determines that a stable dose and regimen of XYWAV is achieved, XYWAV may be taken with or without food. If needed, XYWAV will be titrated to an optimized dose and regimen based on efficacy and tolerability, under the advisement and instruction from the investigator, as described in [Section 8.1.6](#).

Additionally, an optional interim analysis may be conducted without pause in enrollment, as described in [Section 9.5](#).

Objectives and Endpoints:

Table 1 Objectives and Endpoints

Objectives	Key Endpoints
To describe the clinical experience of participants switching from Xyrem to XYWAV for the treatment of narcolepsy with or without cataplexy in terms of safety, tolerability, effectiveness, and treatment optimization.	
 • Adverse Events and Serious Adverse Events • Change in the Nausea Visual Analog Scale • Change in weekly rate of cataplexy attacks (for Narcolepsy Type 1) • Change in Epworth Sleepiness Scale to assess excessive daytime sleepiness • Participant Global Impression of Change • Time to optimized dose and regimen • Number of changes from first dose and regimen to optimized dose and regimen • Number of participants dosing fasted versus dosing without consideration of food • Timing and characterization of meals relative to dosing
Exploratory Objectives	Exploratory Endpoints
To describe the ease of conversion and participant preference of XYWAV in participants with narcolepsy with or without cataplexy	
 • Ease of Switching Medications Scale • Forced Preference Questionnaire

Overall Design:

[figure not shown]
Study JZP258-401 is a multi-center, open-label, single-arm, phase 4 clinical trial designed to describe the clinical experience of participants switching from Xyrem to XYWAV in terms of safety, tolerability, effectiveness, and optimization of treatment.

Table 2 Overall Study Design

Overall Design	
Study Phase	Phase 4
Clinical Indication	Narcolepsy
Study Type	Interventional
Type of Design	Open-label, single-arm, multicenter study for conversion and treatment optimization from Xyrem to XYWAV
Type of Control	None
Study Blinding	Open-label
Population	Participants with narcolepsy
Number of Participants	An estimated total of 100 participants will be enrolled
Duration of Participants	
The study starts from the time participants sign the informed consent form (ICF) through the end of the study procedures/contact. Estimated study duration spanning from first participant in (FPI) to last participant out (LPO) / last follow-up visit is 17 months.
 
For each participant the estimated duration from consent to completion is 14 weeks. The study is comprised of the following 4 distinct periods:
 
 • Screening period (up to 30 days) • Baseline (Xyrem-stable dose and regimen) period (2 weeks) • Intervention (Open-label Conversion and Treatment Optimization) period (6 weeks) • Safety Follow-up period (2 weeks)
Number of Treatment Arms	1
Treatment Groups	
XYWAV
 
(XYWAV started on the same dose [gm-per-gm] and regimen as Xyrem and subsequently stabilized and optimized to an effective dose [up to a maximum nightly dose of 9 grams] and regimen, at investigator's discretion)

Data Monitoring Committee	A data monitoring committee is not planned for this study.

1.2. Schema

Figure 1 Schematic Representation of Overall Design of Study JZP258-401

*Adjustment to achieve optimal clinical benefit, with adequate control of cataplexy and EDS while maintaining tolerability per investigator judgment.

Abbreviations: EDS = excessive daytime sleepiness; wks = weeks

1.3. Schedule of Activities (SoA)

Table 3 Schedule of Assessments

Procedure	Screening Period (Up to 30 days before Day 1)	Baseline Period	Intervention Period (Open Label Conversion and Treatment Optimization Period)		Discontinuation (E/D) ³	Safety Follow-up Period
			Conversion from Xyrem to XYWAV ¹	Treatment Optimization on XYWAV ²		
Visit (V) Number ⁴	V1	V2	V3	V4 Clinic Visit	V5, V6 Phone Call	V7 Clinic Visit
Visit Window +/- Day or End of Week (W)	Day -30 to -1	Day 1 + 1 day	Day 15 + 3 days	W3 + 3 days	W4, W5 + 3 days	W6 + 3 days
Informed Consent	X					W10 +3 days
Inclusion/Exclusion Criteria	X	X				
Demographics	X					
Medical History	X	X				
Physical Examination	X					
Vital Signs (BP, HR, body temperature, RR)	X	X	X	X	X	X
Comprehensive metabolic panel, hematology, UA, TSH	X					
Urine Drug Screen	X	X	X		X	X
Alcohol Screen	X	X	X		X	X
Serum Pregnancy Test	X					

Procedure	Screening Period (Up to 30 days before Day 1)	Baseline Period	Intervention Period (Open Label Conversion and Treatment Optimization Period)			Discontinuation (E/D) ³	Safety Follow-up Period
			Conversion from Xyrem to XYWAV ¹	Treatment Optimization on XYWAV ²	End of Treatment (ET) ³		
Visit (V) Number ⁴	V1	V2	V3	V4 Clinic Visit	V5, V6 Phone Call	V7 Clinic Visit	V8
Visit Window +/- Day or End of Week (W)	Day -30 to -1	Day 1	Day 15 + 1 day	W3 +3 days	W4, W5 +3 days	W6 +3 days	W8 +3 days
Electrocardiogram	X						
Cataplexy Frequency Diary; Assess control of cataplexy (Appendix 5)	X ⁵	X	X	X	X	X	X
Review/discuss participant diaries for completeness	X	X	X	X	X	X	X
Nausea Visual Analog Scale (Appendix 6)		X ⁶			X ⁶	X ⁶	
Epworth Sleepiness Scale; Assess control of EDS	X					X	X
Forced Preference Questionnaire (Appendix 9)						X	X
Ease of Switching Medications Scale (Appendix 8)						X	X

Procedure	Screening Period (Up to 30 days before Day 1)	Baseline Period Xyrem-Stable Dose and Regimen	Intervention Period (Open Label Conversion and Treatment Optimization Period)			Discontinuation (E/D) ³	Safety Follow-up Period
			Conversion from Xyrem to XYWAV ¹	Treatment Optimization on XYWAV ²	End of Treatment (ET) ³		
Visit (V) Number ⁴	V1	V2	V3	V4 Clinic Visit	V5, V6 Phone Call	V7 Clinic Visit	V8
Visit Window +/- Day or End of Week (W)	Day -30 to -1	Day 1	Day 15 + 1 day	W3 +3 days	W4, W5 +3 days	W6 +3 days	W8 +3 days
Participant Global Impression of Change						X	X
Columbia-Suicide Severity Rating Scale Screening (Baseline version)	X						
Participant Health Questionnaire-9	X						
Adverse Events and Serious Adverse Events Reporting (Appendix 7)	X	X	X	X	X	X	X
Concomitant Medications	X	X	X	X	X	X	X
Food and Drug Dosing Diary (Appendix 4)	X ⁵	X	X	X	X	X	X
Assess diary for completeness and compliance after start of dosing							

Procedure	Screening Period (Up to 30 days before Day 1)	Baseline Period	Intervention Period (Open Label Conversion and Treatment Optimization Period)		Discontinuation (E/D) ³	Safety Follow-up Period
			Conversion from Xyrem to XYWAV ¹	Treatment Optimization on XYWAV ²		
Visit (V) Number ⁴	V1	V2	V3	V4 Clinic Visit	V5, V6 Phone Call	V7 Clinic Visit
Visit Window +/- Day or End of Week (W)	Day -30 to -1	Day 1	Day 15 + 1 day	W3 +3 days	W4, W5 +3 days	W6 +3 days
Dispense study drug			X		X	
Collect study drug, measure compliance					X	X

Abbreviations: BP = blood pressure; EDS = excessive daytime sleepiness; HR = heart rate; RR = respiratory rate; TSH = thyroid-stimulating hormone; UA = urinalysis

1. All participants will begin XYWAV treatment at the beginning of the Intervention (Open-label Conversion and Treatment Optimization) period, starting the night of Visit 3/Day 15 and continue through to the End of Treatment (ET) (Visit 8) or Early Discontinuation (E/D), as applicable.
2. Participants must be on an optimized dose of XYWAV for at least the final 2 weeks of the Intervention Period.
3. Following ET (Visit 8) or E/D, investigators will determine the appropriate course of care with the participant, with the option to resume medications that were discontinued prior to or during study participation.
4. The investigator may have the participant attend an unscheduled visit at any time during the study, if deemed necessary.
5. The participant is expected to start indicated diary completion on the morning after the participant enters the Baseline period (Day 1).
6. NVAS will be captured daily during the last 7 days of the Baseline (Xyrem-stable dose and regimen) period and the last 7 days of the Intervention period (on XYWAV) prior to the ET visit, or prior to the E/D visit, if possible.

2. INTRODUCTION

XYWAV (JZP-258) oral solution has been developed by Jazz Pharmaceuticals (Jazz) as an alternative, low-sodium formulation for Xyrem (sodium oxybate) and was recently approved in the US for the treatment of cataplexy or EDS in patients 7 years of age and older with narcolepsy ([XYWAV USPI 2020](#)).

Xyrem oral solution (0.5 g/mL) has been available in the US since 2002, and is indicated in the US for the treatment of cataplexy or EDS in patients 7 years of age and older with narcolepsy ([Xyrem USPI 2020](#)). Xyrem is also approved in Canada for the treatment of cataplexy in patients with narcolepsy ([Xyrem Canadian Product Monograph 2014](#)), and in the European Union (EU) ([Xyrem EU Summary of Product Characteristics \[SmPC\] 2015](#)) for the treatment of narcolepsy with cataplexy in adult patients.

XYWAV and Xyrem contain the same active moiety, which is the endogenous neuropeptide, gamma hydroxybutyrate (GHB) or oxybate, at the same concentration. However, compared to the sodium oxybate composition of Xyrem, the unique mixed salt formulation of XYWAV (comprised of calcium, potassium, magnesium, and sodium salts of oxybate) results in 92% less sodium – or approximately 1,000 to 1,500 mg/night – than Xyrem, at the recommended dosage range of 6 to 9 grams.

While Xyrem has been proven safe and effective when prescribed per recommended label and has been designated as standard of care for the treatment of cataplexy and EDS by the American Academy of Sleep Medicine (AASM) ([Morgenthaler 2007](#)), the current formulation of Xyrem (sodium oxybate) imposes a significant sodium burden to an individual's diet. The American Heart Association (AHA) and the Food and Drug Administration (FDA) recommend no more than 2300 mg of sodium intake per day, with an ideal limit of no more than 1,500 mg per day for most adults ([AHA 2018](#); FDA 2016). Additionally, an increased risk of cardiovascular disease has been causally associated with high levels of sodium intake (FDA 2016; [National Academies of Sciences, Engineering, and Medicine 2019](#); [Whelton 2012](#)). Administration of the maximum recommended daily dose of Xyrem (9 grams/day), results in an intake of 1.64 grams sodium/day, akin to 109% of the ideal recommended dietary allowance of sodium per day ([CDC 2010](#)).

Excess sodium intake is correlated with increases in blood pressure (BP), hypertension, stroke, and other cardiovascular disease ([Mente 2014](#), [Gardner 2012](#), [Institute of Medicine \[IOM\] 2005](#)).

Epidemiological studies indicate an increased risk of morbidity and mortality from cardiovascular diseases, including coronary heart disease and stroke, with increased sodium intake ([EFSA 2006](#)). The current USPI for Xyrem oral solution includes a warning to monitor patients who are sensitive to salt intake (eg, those with heart failure, hypertension, or impaired renal function), conditions that are common in the narcolepsy population ([Ohayon 2013](#); EFSA 2006).

With the goal of establishing a new standard of care for participants with narcolepsy, the low-sodium formulation of XYWAV has been designed to preserve the same concentration of oxybate as that in Xyrem, but with a significantly reduced sodium load that does not warrant warnings about sodium content. The sodium contribution of XYWAV is approximately 10% of the ideal RDA (compared to sodium levels of 109% RDA in Xyrem). Thus, XYWAV provides the same therapeutic benefits of Xyrem while offering an improved safety profile owing to the reduced sodium content, particularly for participants with sodium-sensitive conditions and those concerned about limiting their daily sodium intake.

The therapeutic efficacy and safety of XYWAV has been demonstrated in a global phase 3 double-blinded, placebo-controlled, randomized-withdrawal, multicenter clinical trial (Study 15-006, NCT03030599), including a 24-week open-label extension (OLE) period, in patients with narcolepsy

([XYWAV USPI 2020](#), [Thorpy 2020](#)). In Study 15-006, which enrolled 201 patients and randomized 134 patients, XYWAV demonstrated significant differences ($p<0.0001$) in the weekly number of cataplexy attacks and Epworth Sleepiness Scale (ESS) scores (a measure of EDS) compared to placebo. Additionally, the safety profile of XYWAV was consistent with that expected for oxybate.

This current study (JZP258-401) is a multi-center, open-label, single-arm, phase 4 trial that seeks to build upon the demonstrated benefits of XYWAV and provide further descriptive evidence of safety, effectiveness, tolerability and treatment optimization in participants switching from Xyrem to XYWAV. The study will include comparative assessments related to treatment-based and exposure-related adverse events (AE), tolerability, and therapeutic effectiveness of disease control between Xyrem and XYWAV. Participants will be switched from Xyrem to XYWAV at the same dose and regimen as Xyrem. Once the investigator determines that a stable dose and regimen of XYWAV is achieved, participants will be allowed to dose with or without food. If needed, XYWAV will be titrated to an optimized dose and regimen based on efficacy and tolerability, under the advisement and instruction from the investigator.

Success in this study will be indicated by seamless switching of the majority of participants from Xyrem to XYWAV, with little or no changes in dose strength or regimen. Additionally, evidence will be provided to support participant preference for XYWAV based on its lower level of sodium, potentially improved tolerability profile, a safety profile typical of oxybate, and similar disease control as participant's current Xyrem dose and regimen. Collectively, these data are expected to expand the knowledgebase of clinical experience in the population of participants with narcolepsy transitioning from Xyrem to XYWAV.

2.1. Study Rationale

Study JZP258-401 is an open-label, single arm, phase 4 interventional trial designed to provide descriptive evidence on the safety, tolerability, effectiveness and optimization of treatment associated with the switching of Xyrem-stable participants with narcolepsy to XYWAV.

The objectives of the study are to delineate the overall clinical experience associated with treatment switching from Xyrem to XYWAV, and evaluate if conversion to XYWAV can be performed with relative ease and rapidity, and with minimal adjustment of dose and regimen. Additionally, the study will collect evidence on whether in comparison with Xyrem, XYWAV offers greater flexibility in dosing with regard to food and improved tolerability for nausea. This study will also evaluate patient preference for the low-sodium formulation of XYWAV relative to that of Xyrem.

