8.2.4. Dose and Regimen Changes in Intervention Period

To evaluate treatment optimization with XYWAV during the Intervention period, the number of changes from the first dose and regimen to an optimized dose and regimen and the time taken to achieve the optimized dose and regimen will be measured, as described in [Section 9.4.2](#).

Additionally, the number of participants dosing fasted versus dosing without consideration of food, and the timing and characterization of meals with regard to dosing will be summarized descriptively. These assessments will utilize participant data collected using a self-administered, electronic Food and Drug Dosing Diary ([Appendix 4](#)) completed by participants daily (Section 9.4.2).

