9.4.2. Effectiveness Endpoints

Effectiveness endpoints will be summarized descriptively. The following effectiveness endpoints will be assessed in this study:

- Change in weekly rate of cataplexy attacks: Participants will be required to complete an electronic Cataplexy Frequency Diary ([Appendix 5](#)) daily. Based on these data, the weekly rate of cataplexy attacks (for NT1) will be established. Additionally the change in weekly cataplexy rate from the last week of the Baseline period (on Xyrem) to that of individual weeks during the Open Label Conversion and Treatment Optimization Period will be summarized. For participants experiencing at least 1 day of cataplexy attack, the weekly number of cataplexy attacks will be derived as the average number of daily attacks from days with non-missing data within the week, multiplied by 7.
- Change in Epworth Sleepiness Scale (to assess EDS): Changes in ESS scores between the Baseline period and ET or E/D, as applicable, will be summarized.
- Participant Global Impression of Change: PGIC values will be measured at the ET or E/D, as applicable, in accordance with the SoA ([Section 1.3](#)). The number of participants with each response will be summarized. Additional categorization of the scores may be performed and summarized.
- Time to optimized dose and regimen is defined as the time from the first dose and regimen to the optimized dose and regimen of XYWAV, where the optimized dose and regimen indicates the final dose and regimen that remains unchanged throughout the remainder of the Intervention (Open-label Conversion and Treatment Optimization) period. Compliance is not considered in the derivation of the time to achieve optimized dose and regimen. The time to achieve optimized dose and regimen will be summarized.
- Additionally, the number of changes from the first dose and regimen to optimized dose and regimen, the number of participants dosing fasted versus dosing without consideration of food, and the timing and characterization of meals with regard to dosing of XYWAV ([Appendix 4](#)) will be summarized descriptively.

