APPENDIX 4. FOOD AND DRUG DOSING DIARY**A. Drug taken: Xyrem**

Subject Number: _____

Date: _____

1. What was the time of the first dose?

(HH:MM)

2. What was the end time of the last meal prior to the first study drug dose?

(HH:MM)

3. Indicate type of meal below-

- Regular Meal- food consumed as part of dinner or planned occasion
- Snack- a bite to eat consumed between meals or prior to bed
- Beverage- a liquid drink (eg, tea, juice, milk), other than water

B. Drug taken: XYWAV

Subject Number: _____

Date: _____

1. What was the time of the first dose?

(HH:MM)

2. What was the end time of the last meal prior to the first study drug dose?

(HH:MM)

3. Indicate type of meal below-

- Regular Meal- food consumed as part of dinner or planned occasion
- Snack- a bite to eat consumed between meals or prior to bed
- Beverage- a liquid drink (eg, tea, juice, milk), other than water

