9. EFFECTIVENESS

9.1. Key Effectiveness Endpoints and Analysis

Unless otherwise specified, effectiveness data will be primary summarized using both the XYWAV Safety Analysis Set and XYWAV Efficacy Analysis Set.

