9.1.5. Characterization of Meals Relative to Dosing

Once a participant has reached optimized dose and regimen, the investigator may decide to instruct the participant to dose without regard to food. The number of participants and percentage in each group (fasted versus without consideration of food), tabulation of the food types (regular meal, snack, drink) and percentage will be summarized.

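### The planned meal summary has no Xyrem side, so it cannot address the comparison with Xyrem on food flexibility that Protocol 2.1 sets out

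*Protocol*

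**What the plan says.** **The question.** Protocol 2.1 states that "the study will collect evidence on whether in comparison with Xyrem, XYWAV offers greater flexibility in dosing with regard to food", and in the same sentence names improved tolerability for nausea. Protocol 4.1 adds that the dosing information may be used to support dosing XYWAV with or without food, and may enter label discussions.

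**The data.** Appendix 4 has a part A, headed "Drug taken: Xyrem", and a part B for XYWAV. Both ask for the time of the first dose, the end time of the last meal before it, and the type of intake. The diary is "completed by participants daily" (Protocol 8.2.4). The footnote to the Schedule of Activities gives its start: "The participant is expected to start indicated diary completion on the morning after the participant enters the Baseline period (Day 1)".

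**The analysis.** Protocol 9.4.2 says that "the timing and characterization of meals with regard to dosing of XYWAV" will be summarized descriptively. SAP 9.1.5 opens: "Once a participant has reached optimized dose and regimen, the investigator may decide to instruct the participant to dose without regard to food". It then specifies: "The number of participants and percentage in each group (fasted versus without consideration of food), tabulation of the food types (regular meal, snack, drink)", with percentages. It names no Xyrem baseline, no change and no paired contrast. SAP 9.1 says that "effectiveness data will be primary summarized using both the XYWAV Safety Analysis Set and XYWAV Efficacy Analysis Set".

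**The concern.** A comparison with Xyrem needs a Xyrem side. The plan collects one and then specifies no food analysis for it. A percentage observed on XYWAV has two components: participants who already ate close to the dose on Xyrem, and participants who began to do so after the switch. Only the second bears on the question in Protocol 2.1, and the planned tables do not separate the two.

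The food data have a stated onward use (Protocol 4.1), and interim data may be presented externally (Protocol 9.5). A one-sided percentage could then stand next to comparative wording that it does not support, although the data needed for a two-sided description are already in the diary.

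**Working it through.** There is no planned figure to reproduce. The sample of about 100 rests on no formal calculation (Protocol 9.2), and no food rates are given. The check is mainly textual.

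**1. Is a Xyrem-to-XYWAV change specified where it is intended?** Compare the endpoints:

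| Endpoint | Xyrem baseline defined | Change specified |
|---|---|---|
| Nausea scale (SAP 10.8) | Yes, last 7 days of Baseline | Yes, with 95% CI of the mean change |
| Cataplexy rate (SAP 9.1.1) | Yes, last week of Baseline | Yes |
| ESS (SAP 9.1.2) | Yes | Yes |
| Meals relative to dosing (SAP 9.1.5) | No | No |

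The baseline characteristics in SAP 8.3 include cataplexy rate and ESS but no meal pattern. SAP 7.6 lists no change to the meal analysis.

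**2. Do general provisions fill the gap?** SAP 7.1 allows summaries by visit or study period where applicable, and SAP 7.4 mentions a 95% CI for a difference in proportions as an example. Neither is tied to this endpoint. Neither sets a meal-to-dose interval, a threshold or a pairing rule. The analysis sets in SAP 9.1 do not settle the matter, because the cataplexy and ESS changes use the same sets and still draw on Baseline data.

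**3. How much data is involved?** Baseline is 2 weeks and the Intervention period 6 weeks. With 100 participants and complete diaries:
- Xyrem: 100 × 14 = 1,400 nights
- XYWAV: 100 × 42 = 4,200 nights

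These are upper figures, since dropout and missed entries reduce both.

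**4. What can a XYWAV-only percentage hide?** Assume that 40% dose without consideration of food on XYWAV, with N = 100. Alone, this gives 40% ± 1.96 × √(0.4 × 0.6/100) = 40% ± 9.6, or 30% to 50%, whatever happened on Xyrem. For the paired difference d, with p01 the share changing towards eating near the dose and p10 the share changing away, SE = √[(p01 + p10 − d²)/N].

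| Assumed share on Xyrem | Increase d (points) | 95% CI if all on Xyrem continue | 95% CI if periods are independent |
|---|---|---|---|
| 0% | 40 | 30.4 to 49.6 | 30.4 to 49.6 |
| 10% | 30 | 21.0 to 39.0 | 18.7 to 41.3 |
| 20% | 20 | 12.2 to 27.8 | 7.6 to 32.4 |
| 30% | 10 | 4.1 to 15.9 | −3.1 to 23.1 |
| 40% | 0 | nobody changes | −13.6 to 13.6 |

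The same 40% fits an increase anywhere from 0 to 40 points.

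**5. How precise would a paired summary be?** Assume 5% change the other way (p10 = 0.05) and N = 100:
- d = 0.20, p01 = 0.25: 1.96 × √[(0.30 − 0.04)/100] = 10.0 points
- d = 0.30, p01 = 0.35: 1.96 × √[(0.40 − 0.09)/100] = 10.9 points
- d = 0.40, p01 = 0.45: 1.96 × √[(0.50 − 0.16)/100] = 11.4 points

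These half-widths are for a yes/no classification per participant. For a mean difference in percentage of nights, the half-width is about 1.96 × SD/√100 = 0.196 × SD. The documents give no SD.

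**The case against.** **The comparison is only rationale text.** The formal objective is to describe the switching experience. The Introduction lists AEs, tolerability and disease control as the comparative assessments, without food, and there is no hypothesis test. This lowers the weight of the point and rules out asking for a test. It does not remove the statement in 2.1, and a descriptive study can still describe both periods.

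**The SAP is silent rather than restrictive.** This stands in part. XYWAV-only is explicit in Protocol 9.4.2 but only implied in SAP 9.1.5, and the key endpoint itself names no drug. An analyst could add a Xyrem table under SAP 7.1, but nothing requires it, and a table by period would still not show within-participant change.

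**The label statement in Protocol 4.1 is about XYWAV alone.** Correct: it does not need a Xyrem comparison. The sentence in 2.1 does.

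**A paired shift would not isolate the drug.** This stands and limits the remedy. Protocol 4.3 and 8.1.6 apply the 2-hour wait as with Xyrem, and it is lifted on XYWAV only once the investigator allows it. A within-participant shift mixes the new instruction with any property of the drug.

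**A stronger reading to avoid.** A reader might infer that the plan credits existing Xyrem habits to XYWAV as a gain. The documents do not support that. They specify counts and percentages and compute no gain. Nor are participants who stay fasted wholly invisible, since SAP 9.1.5 counts a fasted group.

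**Conclusion.** The gap holds as a mismatch between a stated comparison and the specified analysis. Protocol 2.1 asks about food flexibility relative to Xyrem, the diary collects both sides, and the specified meal summary covers XYWAV explicitly in the protocol and by implication in the SAP. Followed as written, it cannot distinguish habits carried over from Xyrem from a change after the switch, so it cannot address that comparison.

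No document-based size can be given. The range of 0 to 40 points rests on an assumed 40% on XYWAV and 0% to 40% on Xyrem. The half-widths of about 10 to 11 points rest on assumed changes and 100 participants with diary data on both drugs. The true Xyrem rate may be low, given the 2-hour instruction, but that is unverified and part A would show it.

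This should be corrected, but it does not threaten the study's formal objective. Even when corrected, the result describes a change in dosing behaviour and not a drug effect.

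**What to change.** In SAP 9.1.5, recorded in SAP 7.6 as a change from Protocol 9.4.2:

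1. Derive the meal-to-first-dose interval and the intake type by one rule for Xyrem nights (part A) and XYWAV nights (part B). State which XYWAV nights count and how a participant is assigned to fasted or without consideration of food. The diary has no item for the latter, and SAP 9.1.5 gives no rule.
2. In participants with diary data on both drugs, report descriptively the percentage of nights with an interval under 2 hours in each period, the within-participant difference with 95% CI, and a shift table from Xyrem category to XYWAV category. This would also supply the meal-timing summary that the key endpoint names and SAP 9.1.5 omits.
3. State with the table that the difference reflects the changed meal instruction as well as the drug.
4. Reconcile the trigger for the food allowance, which the protocol ties to a stable dose and SAP 9.1.5 to an optimized dose, because it affects which nights are comparable.

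If this is not done, remove the comparative wording on food from Protocol 2.1.

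The cost is SAP text and one table, with no new data. The alternative changes the protocol and would need IRB/IEC approval under Protocol 10.1.1, so the SAP route is the lighter one.
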